10.3.2 Pharmacodynamics

PD data will be analysed as appropriate depending on the biomarker being studied and the assay employed.

10.3.3 Pharmacokinetics

PK parameters will be derived from sample data, including peak plasma concentration (C_{max}), time to reach C_{max} (T_{max}), elimination half-life ($T_{1/2}$), area under the curve from zero to the time of last quantifiable concentration (AUC_{0-t}) and AUC extrapolated to infinite time (AUC_{∞}). In addition, comparison between single dose and multi-dose PK parameters will be made for assessment of steady-state drug accumulation.

Bioanalysis will be performed by Covance UK. PK samples will be analysed for all patients in Part A, with a minimum of 2 patients/cohort analysis available to inform the assessment of patient safety and dose reviews.

The Correlation between the PK parameters derived and DLT or non-DLT toxicity at each dose level. Calculation of a correlation coefficient will determine the significance.

10.3.4 Response evaluation:

The best tumour response evaluation as determined radiologically or clinically will be presented as proportions. Part A and B patients undergo response assessment every 8 weeks (2 cycles), the first response assessment is therefore at 8 weeks, and they continue after that at 8 weekly intervals unless there is clinically measurable progression or toxicity. The association of the pharmacodynamics biomarkers with treatment response will be explored.

10.3.5 Expansion cohorts (Part B):

The tolerability, PD parameters and tumour response data will be evaluated as stated above for each melanoma cohort separately.

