6.6 Dose escalation scheme

Patients will be enrolled to ensure a minimum of 3 and a maximum of 6 evaluable patients per cohort. The dose level of CCT3833 will be assigned using all available data by the Sponsor in conjunction with the Safety Review Committee (SRC). Dose assignment will be made after considering the number of patients already enrolled at the current dose level, the number of DLTs (and any other drug related AEs) observed at the current dose level, and the number of patients enrolled who are at risk of developing a DLT.

The first patient in all cohorts will be treated for 7 days taken from Day 1, before the second and third patients can take their first dose of CCT3833 in parallel. Patients who receive less than 75 % of their planned doses in Cycle 1, taken from Day 1 onwards, for reasons other than toxicity will not be evaluable for assessment of DLT for dose review decisions and will be replaced in the cohort.

In order to make the decision to escalate the CCT3833 dose, three evaluable patients must have completed one cycle of treatment (28 days). The time between cohorts is therefore approximately 6 weeks.

The dose increases between cohorts will be up to 100%, i.e. doubling of the dose (dosed on a flat scale and not by body weight or body surface area), until a probable or highly probable drug-related CTCAE v4.03 (Appendix 4) Grade 3 AE (or grade 4 haematological toxicity) is reported. Subsequent dose increases between cohorts will be driven by reported safety data and available PK and PD data. The available PK data for all patients will be reviewed as part of the dose escalation data. PK data for a minimum of two patients in the current cohort will be required to inform dose review decisions. PK data for a minimum of two patients from the previous cohort will also be required.

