6.8 Dose escalation decisions

An SRC meeting will be triggered when three patients have had the opportunity to complete the first cycle of treatment. The safety data including a list of DLTs and all AEs will be reviewed, along with all other available data (including PK analyses from at least two subjects), in order to make the decision. When sufficient data are available to assess the existing cohort, the next dose level will be assigned according to the following:

- Proceed with dose escalation: If the data is available from three patients who have been treated in a cohort and no DLTs have been observed at that dose level, then dose escalation can be considered.
- Expand the cohort to further explore the dose level: If the data is available from three patients who have been treated in a cohort and one DLT has been observed at that dose level, then the cohort will be expanded to include six patients.
- De-escalate the dose: If two DLTs have been observed at any dose level, the dose will be de-escalated to either the previous dose level (expanding to include up to six patients) or an intermediate dose level will be explored. If the previous dose level already included a cohort of six patients then this will be identified as the MTD.
- Explore different dosing schedules or formulations: If the daily continuous dosing treatment schedule is not tolerated, then the frequency of dosing for subsequent patients may be reduced. Dose escalation will continue at the reduced schedule.
- Stop the dose escalation phase of the study.

The decisions of the SRC on the next dose level and/or dosing schedules will be documented and provided to the Investigators prior to dosing any new patients.

The RP2D to be further evaluated in Part B (expansion phase) will be determined by the SRC based on the MTD and observed safety profile, PK and PD data. During the expansion phase, the SRC will continue to monitor safety and will agree any action needed to refine the dose or dosing schedule.

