8.1.2 On-treatment assessments

8.1.2.1 Pharmacokinetic evaluations

During the dose escalation phase of the study, patients will be admitted (or required to stay close) to the clinical research facility for the administration of the first single dose (at Day -7 to Day -3) and thereafter for 48 hours, to allow blood sampling for PK to be collected. A second admission will also be required for 24 hours from Cycle 2, Day 1 (\pm 3 days), to allow further PK sampling (including patients that have inpatient dose escalation). Patients will be advised of a standard meal (600 – 700 kcal) to be consumed prior to dose administration.

The sampling schedule is currently as defined in Table 9 below, but may be adjusted later if the emerging PK data suggest alternative time points would be more informative. Data will be used to determine PK parameters including:

- C_{max}
- T_{max}
- AUC_{0-t}
- AUC_{inf}
- $T_{1/2}$

Table 9: PK sampling schedule

Days (D)	Sample times (in hours) relative to dose*	Period of sampling relative to dose
Single dose (D-7 to D-3)	0	Pre-dose
Single dose (D-7 to D-3)	0.25, 0.5, 1, 1.5, 2, 3, 4, 6, 8, 12, 24, 48	Post-dose
Cycle 2, Day 1-2 (± 3 days) ⁺	0	Pre-dose
Cycle 2, Day 1-2 (± 3 days) ⁺	0.25, 0.5, 1, 1.5, 2, 3, 4, 6, 8, 12, 24	Post-dose

* ± 5 min for first hour, ± 10 min for 1.5-3 hours, ± 15 min for 4-8 hours, ± 1 hour for 12 hours, ± 2 hours for 24/48 hour samples.

⁺The same sampling schedule and timepoint will be used for patients that are dose escalated on C2D1 of the increased dose

At each timepoint, 4 mL of blood will be collected into 4 mL K₂EDTA tubes. Sample processing, storage and shipment details will be described in the Laboratory Manual.

Bioanalytical analysis of plasma levels of CCT3833 will be performed by Covance UK. Samples for fast-turnaround analysis (supporting dose escalation decisions) will be analysed and quality controlled data generated within 48 hours from receipt of samples. This data will be analysed by a PK specialist, taking a further 24 hours to generate preliminary PK parameters and interpretation for use in the dose escalation meetings. Definitive PK parameter generation, using actual elapsed blood sampling times, will be performed upon release of final bioanalytical data. Any unused samples will be retained at ICR or another laboratory for possible metabolic profiling assessments to be reported separately.

Additional evaluations to be performed during the PK admissions are as follows:

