10.2 Sample size

The sample size for this Phase 1 trial is not based on a formal sample size calculation as no formal statistical hypothesis is being tested. The total number of patients has been based on the desire to obtain adequate tolerability, safety, pharmacokinetic and pharmacodynamics data while exposing as few patients as possible to the IMP and procedures. The total number of patients required will depend upon the toxicities encountered and the number of dose cohorts required.

In Part A, the minimum number of patients will be 3, if there are 2 DLTs at the starting dose. The maximum number of patients is expected to be 42.

In Part B, there are 3 different patient cohorts each including 9 recruited patients, leading to a maximum of 27 patients within the expansion phase. An additional small number of patients from Part A may continue on treatment into Part B if they meet the inclusion criteria. These patients will be in addition to the 27 new patients recruited to Part B.

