10.3 Statistical analysis

All quantitative data will be presented as number of observations, mean, standard deviation, minimum and maximum values. Qualitative data will be presented as number of observations and percentages. When appropriate, data will be presented together with 95% confidence intervals.

Baseline characteristics will be summarised for all enrolled patients. Patients who died or withdrew before treatment started or did not complete the required safety observations will be described and evaluated separately. Treatment administration will be described for all cycles. Dose administration, dose modifications or delays and the duration of therapy will be described.

The trial aims to determine the following endpoints:

Primary:

- a. Establishing the MTD and RP2D of CCT3833 (Part A only)
- b. Assess the safety and tolerability profile of CCT3833 (Part A and B)

Secondary:

- a. Establish pharmacokinetic parameters using the plasma levels of CCT3833 (Part A only)
- b. Measure response using radiological/clinical criteria (Part A and B)
- c. Determine the correlation between pharmacokinetic parameters and tolerability (Part A only)

Exploratory:

- a. Measurement of pharmacodynamics biomarkers (Parts A and B)
- b. Determine the magnitude and duration of effect of PD biomarkers (Parts A and B)

10.3.1 Safety and toxicity:

Safety data will be collected from the date of written consent. Safety variables will be summarised by descriptive statistics. The number and percentage of patients experiencing DLT or non-DLT toxicity in each dose level will be tabulated and the number of cohorts recruited in Part A will be recorded, respectively. AEs will be coded using MedDRA and reported for each dose level and presented as tables of frequency of AEs by body system and by worst severity grade observed. Tables should indicate related and unrelated events. The number and percentage of toxicity grades 1-4 and grade 3-4 respectively, experienced by those patients recruited in Part B will be reported. Laboratory data will be presented by dose level at each observation time. Values outside normal limits will be identified and summarised by frequency distribution.

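### The PK-toxicity correlation is planned within dose levels of 3 to 6 patients, where for DLT it is undefined or, by exact test, cannot reach 5%; pool it over Part A, and define the accumulation ratio.

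*Combined protocol and SAP*

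**What the plan says.** Section 10.3.3 describes the exposure-toxicity analysis in two sentences. The first has no verb: "The Correlation between the PK parameters derived and DLT or non-DLT toxicity at each dose level". The second is "Calculation of a correlation coefficient will determine the significance". No type of coefficient, significance level, pooling rule or multiplicity rule is given. The general text of Section 10.3 says that, where appropriate, "data will be presented together with 95% confidence intervals".

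The size of a dose level comes from Section 6.6: "Patients will be enrolled to ensure a minimum of 3 and a maximum of 6 evaluable patients per cohort". Section 6.8 says that if data are available from three patients and "no DLTs have been observed at that dose level, then dose escalation can be considered". Section 6.5 ends escalation at two or more DLTs at a level.

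The endpoint served is secondary. Table 6 links it to finding a safe therapeutic range, and Section 10.3, secondary item (c), assigns it to Part A. Neither confines it to a dose level.

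On accumulation, Section 10.3.3 says that a "comparison between single dose and multi-dose PK parameters will be made for assessment of steady-state drug accumulation". The AUCs listed are AUC0-t, to the last quantifiable concentration, and AUC to infinity. Table 9 sets the post-dose single-dose samples at "0.25, 0.5, 1, 1.5, 2, 3, 4, 6, 8, 12, 24, 48" hours; the Cycle 2 Day 1 profile stops at 24 h.

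**The concern.** Read naturally, the text asks for a separate correlation in each small cohort. A level cleared with no DLTs has a constant DLT indicator, so it has no coefficient. A level with one DLT gives a coefficient that rests on one patient. Fixing the dose also discards most of the exposure range, which escalation in steps of up to 100% is there to create. An analysis run as written would therefore say little about the safe therapeutic range, and a non-significant result could be misread as evidence that exposure does not matter.

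The accumulation sentence has a smaller problem. It does not say which parameter, or which interval, is compared between the two profiles, and the AUC0-t windows differ.

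**Working it through.** The plan gives no power, alpha or detectable effect for this analysis, so there is no stated figure to reproduce. Two-sided 0.05 is assumed, in line with the 95% intervals in Section 10.3.

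**DLT within a level, exact tests.** With k DLTs in n patients there are C(n,k) equally likely arrangements under no association. A rank test has a two-sided floor of 2/C(n,k). A permutation test on |r| has a floor of 1/C(n,k), except when k = n/2: the mirror arrangement then gives the same |r| and the floor is 2/C(n,k).

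| DLTs | C(n,k) | Permutation on \|r\| | Rank test |
|---|---|---|---|
| 0 in n | – | undefined | undefined |
| 1 in 3 | 3 | 0.33 | 0.67 |
| 1 in 6 | 6 | 0.17 | 0.33 |
| 2 in 6 | 15 | 0.067 | 0.13 |
| 3 in 6 | 20 | 0.10 | 0.10 |

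No combination with n up to 6 goes below 0.067.

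**How often it is undefined.** Every level with 0 DLTs is undefined; this needs no simulation. As an illustration, three assumed DLT curves over seven levels (42/6 = 7) were simulated, with risk rising from 1–2% at the lowest level to 40–70% at the highest. The undefined share was 68–78% of levels if cohorts start at 3 and expand to 6, and 53–67% if every level enrols 6.

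**Parametric r.** Critical |r| = t/√(n−2+t²), with t the 97.5% point on n−2 degrees of freedom.
- n=3: 12.706/√(1+161.4) = 0.997
- n=4: 0.950
- n=5: 0.878
- n=6: 2.776/√(4+7.71) = 0.811

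If DLT patients' exposure is shifted by 2 SD (an assumption), simulated power is about 10% for 1 in 3, 29% for 1 in 6 and 42% for 2 in 6.

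**Graded non-DLT toxicity.** With no ties, the smallest two-sided Spearman p is 2/n!: 0.33 (n=3), 0.083 (n=4), 0.017 (n=5), 0.003 (n=6). Ties in grade raise these floors.

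**Pooling.** The critical |r| falls to 0.433 at n=21 and 0.304 at n=42. The exact floor stops mattering: for 3 DLTs in 21, C(21,3) = 1330 and the rank floor is 2/1330 = 0.0015.

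**Accumulation.** Take a one-compartment model with fast absorption and x = 2^(−24/t½). The like-for-like AUC0-24 ratio is 1/(1−x). Dividing the steady-state AUC0-24 by a single-dose AUC0-48 gives 1/(1−x²). The second is the first multiplied by 1/(1+x).
- t½ 3.89 h (Table 1, dog-based): x = 0.0139; 1.014 against 1.000, 1% low.
- t½ 7.2 h (Table 1, rodent-based): x = 0.0992; 1.110 against 1.010, 9% low.

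With a 1.2 h absorption half-life (Section 1.2.3 gives 1.22 h in mice and 1.16 h in dogs) the pairs are 1.02 against 1.00 (2% low) and 1.135 against 1.012 (11% low). If the human half-life were longer, which is an assumption, the shortfall would be 20–22% at 12 h and 33–36% at 24 h.

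**The case against.** The strongest reply is that the sentence is loose rather than wrong. It has no verb, Section 10.3.1 uses almost the same dose-level phrase for a tabulation, and the endpoint wording in Table 6 and Section 10.3 allows a pooled analysis. That stands as far as it goes: the objective can be met, and the sponsor may have meant pooling. But Section 10.3.3 does not say so, and an analyst following it would work by level.

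A reader might infer that significance is out of reach for the whole PK-toxicity question. The documents do not support that. The plan names no exact test, and a parametric r can pass 0.811 with a single outlying patient. Non-DLT toxicity is also included and can pass 5% at n=5 or 6. Section 6.8.1 lets intra-patient escalators be counted by the safety review committee. If they were also counted in this analysis, a level could exceed six: 3 DLTs in 8 gives a rank floor of 2/56 = 0.036.

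A reader might also see a contradiction with Section 10.2, where "no formal statistical hypothesis is being tested". That sentence explains the lack of a sample size calculation. Language about determining significance sits awkwardly beside it, but no dose decision in Sections 6.5, 6.6 or 6.8 rests on this correlation.

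On accumulation, a reader might infer that the plan does compare AUCs over unequal intervals and will report too low a figure. It does not say this. The parameter list is open-ended and includes Cmax, both profiles have a 24 h sample from which AUC0-24 can be derived, and AUC0-t ends before 48 h if the drug is no longer quantifiable. Nor does any section say that an accumulation ratio decides the schedule.

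**Conclusion.** The concern holds for the exposure-toxicity analysis as written. Within a dose level of up to 6 patients, the DLT coefficient is undefined whenever there are no DLTs, and no exact two-sided test reaches 5% otherwise (best case 0.067). Parametric and graded versions are possible but weak. These floors follow from the cohort size alone. The undefined shares and power figures rest on the assumed curves and the assumed shift.

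The flaw is in the specified method; the secondary objective remains answerable from the data to be collected. The accumulation point is a clarification only: an unspecified metric that, if taken as AUC0-t, would read about 1 to 11% low at the protocol's own predicted half-lives under a one-compartment model.

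**What to change.** Replace the two sentences in Section 10.3.3 with one exploratory analysis pooled over all Part A patients. For example, regress Cycle 1 DLT on log single-dose AUC0-24 or log Cmax by Firth or exact logistic regression. Use single-dose exposure because Section 6.9.1 reduces the dose after a DLT, so Cycle 2 Day 1 exposure would partly be a consequence of the toxicity. Analyse non-DLT toxicity separately. Report estimates with 95% confidence intervals, and delete the statement that the coefficient determines significance.

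Add AUC0-24 to the parameter list for both PK days. Define accumulation as the within-patient ratio AUC0-24 (Cycle 2 Day 1) / AUC0-24 (single dose), in patients at an unchanged dose, summarised as a geometric mean ratio.

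The cost is a few lines of text, with no new samples or visits. The price is a less definitive-looking statement: with few DLTs the interval will be wide, and pooling does not guarantee power.

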10.4 Timing of analyses

Toxicity data will be reviewed by the SRC prior to any decision regarding dose escalation or opening of new dose cohorts.

The final analysis will be conducted after one of the following conditions is met:

- The study is terminated early (for example, due to toxicity).
- All patients have had the opportunity to receive 12 cycles of treatment and are either continuing with treatment or have completed their 'Off-study' visit (i.e. 14 days (± 7 days) after the last dose of CCT3833).
- N.B. All patients are allowed to continue with CCT3833 treatment beyond 12 cycles if they are receiving therapeutic benefit.

Once one of the conditions is met, a data cut-off date will be established. All patient visits occurring on or before this date will be analysed and summarised in the final clinical study report. Any data collected after this date will be summarised in a supplemental report.

11 ADMINISTRATION AND RESEARCH GOVERNANCE

This trial will be conducted under a clinical trial authorisation (CTA). Approval from the Medicines and Healthcare products Regulation Agency (MHRA) and the relevant Research Ethics Committees will be obtained before the start of this trial. This trial is co-sponsored by the Royal Marsden NHS Foundation Trust and the Institute Of Cancer Research. Applicable regulatory requirements are described in this section.

11.1 Protocol deviations and amendments

Amendments to the protocol may only be made with the approval of the Sponsor, CI, site PIs and statistician. A protocol amendment will be subject to review by the Sponsor before obtaining relevant approvals. Ethics Committee favourable opinion (and MHRA approval if appropriate) will be obtained by the CI before the amendment can be distributed to sites and implemented.

11.2 Completion of the electronic case report form

The Investigators are responsible for ensuring the accuracy, completeness, clarity and timeliness of the data reported in the eCRFs.

Only the Investigator and those personnel who have completed the Study Team Responsibilities Delegation Log as authorised by the PI, should enter or change data in the eCRFs. All protocol required investigations must be reported in the eCRF. The Investigators must retain all original reports, traces and images from these investigations for future reference. The data will be entered in a clinical trials database (Macro V4).

The eCRF will be signed electronically by the Investigator or by an authorised staff member. Study specific information will be entered into an eCRF on a regular basis (ideally after each patient visit). Data that are derived should be consistent with the source documents or the discrepancies should be explained. All eCRF data should be anonymous, ie identified by study patient number only.

Once data has been entered by the site personnel on the eCRF, the data will be reviewed and checked for error and inconsistencies by data management staff at the CTU.

Once the patient is 'off study' and the eCRF has been fully completed, the Investigator must provide a signature to authorise the complete subject data.

11.3 Trial performance and monitoring

11.3.1 Management of the study

The RM-CTU will be responsible for the day to day coordination and management of the trial. This includes all duties relating to pharmacovigilance in accordance with section 9. The RM-CTU will act as custodian of the eCRF data on behalf of the Sponsor.

Before the trial can be initiated, the prerequisites for conducting the trial must be clarified and the organisational preparations made with the trial centres. RM-CTU must be informed immediately of any change in the personnel involved in the conduct of the trial.

During the trial the RM-CTU is responsible for monitoring data quality in accordance with relevant standard operating procedures (SOPs). Before the trial start, the Investigator will be advised of the anticipated frequency of the monitoring visits. The Investigator will receive reasonable notification before each monitoring visit.

It is the responsibility of the Sponsor to

- Review trial records and compare them with source documents
- Check pharmacodynamic samples and storage
- Discuss the conduct of the trial and any emerging problems with the Investigator
- Check that the drug storage, dispensing and retrieval are reliable and appropriate, and
- Verify that the available facilities remain acceptable.

All unused drug supplied must be returned to the supplier or destroyed at the Investigator site by an authorised person who will provide signed confirmation of destruction.

It is the responsibility of the Sponsor to inform the REC within 90 days of the 'end of the trial' (i.e. last patient study visit) that the trial has closed.

